10.1.2 Adverse Device Effect (ADE)

Any untoward and unintended response to a medical device. This definition includes any event resulting from insufficiencies or inadequacies in the instructions for use or the deployment of the device. This definition includes any event that is a result of a user error:

10.1.3 Serious Adverse Event (SAE)

A serious adverse event is an adverse event that:

(1) Led to death

(2) Led to a serious deterioration in the health of the subject that:

- Resulted in life-threatening illness or injury (the patient was at substantial risk of dying at the time of the adverse event or it is suspected that the use or continued use of the product would result in the patient's death);
- Resulted in permanent impairment of a body function or permanent damage to body structure; or necessitates medical or surgical intervention to preclude permanent impairment of a body function or permanent damage to a body structure;
- Required in-patient hospitalization or prolongation of existing hospitalization;
- Resulted in medical or surgical intervention to prevent permanent impairment to body structure or a body function.

10.1.4 Serious Adverse Device Effect (SADE)

A Serious Adverse Device Effect is an Adverse Device Effect that has resulted in any of the consequences characteristic of a SAE or that might have led to any of these consequences if suitable action had not been taken or intervention had not been made or if circumstances had been less opportune.

10.1.5 Relatedness

Investigators are also responsible to categorize adverse events according to their relatedness. The definitions for relatedness classifications are included below.

10.1.5.1 Surgical Procedure Related

Surgical procedure related adverse events are those that are related or possibly related to the procedures involved in the CelonProSleep plus or those normally associated with a surgical procedure. These events typically occur within 10 days of treatment.

10.1.5.2 Other Surgical Procedure Related

Other surgical procedure related adverse events are those that are normally associated with a surgical procedure, but the surgical procedure was not associated with the CelonProSleep plus.

10.1.5.3 Pre-existing or Independent Condition Related

Any event, although temporally associated, that was attributable to a preexisting or independent condition.

10.1.5.4 Other

Any event that cannot be classified in any of the above categories.

10.2 AE Definitions for Sponsor Classification

10.2.1 Unanticipated Adverse Device Effect (UADE)

Any serious adverse effect on health or safety or any life threatening problem or death caused by, or associated with, a device, if that effect, problem, or death was not previously identified in nature, severity, or degree of incidence in the CIP or application (including a supplementary plan or application), or any other unanticipated serious problem associated with a device that relates to the rights, safety, or welfare of subjects..

10.2.2 System component-relatedness

Adverse events that are System-related will be further assessed by the Sponsor according to whether the event resulted from the presence or performance of the surgeon.

10.3 Adverse Event Adjudication

Upon receipt, adverse event CRFs are reviewed for completeness by the Sponsor and Sponsor will request clarification and/or additional information from the Investigator, when necessary. The Sponsor, with the assistance of the Investigator, will also determine whether an event is reportable to regulatory agencies / competent authorities. A Clinical Events Committee (consisting of independent physicians) will review serious adverse events at regular intervals. The CEC is responsible for reviewing the Investigator's assessment and classification of each event.

10.4 Adverse Event Outcome Status

Adverse Events when reported are assigned an "open" or "closed" outcome status by centers depending on the nature of the event or the corrective action involved. When clinically appropriate, centers should work to close events that may not be resolvable during the term of the investigation. Centers may move outcome status to "closed" or alternatively, add text to the adverse event description at follow-up visit addressing that the adverse event is ongoing but for study purposes and outcome data, the event is considered closed.

An Event is "closed" if the subject/event is fully recovered or partially recovered and no further recovery is expected.

An Event is "open" if the subject/event is partially resolved, unchanged, or worsened, or further recovery is otherwise expected. In the case the Event remains open, continue to follow this Event on an adverse event form at each follow-up visit until the event is closed.

10.5 Notification of Serious Adverse Events

The Investigator will report any SAE to the Sponsor as soon as possible, but not later than 24 hours after the investigator learns of the event. All SAEs should be documented on the Adverse Event Case Report Form and an explanation of any medical treatment administered or surgical intervention should be provided. The form must be completed, signed and sent by fax to the Sponsor within 24-hours of learning of the adverse event.

The SAE report must be followed by a full written report

10.6 Subject Deaths

A subject death during the study must be reported to Sponsor as soon as possible. IRB regulations and/or Ethics Committee requirements may require notification of the study Sponsor within 24 hours of learning about the event. The center's IRB/MEC must be notified of any deaths in accordance with that center's IRB/MEC policies and procedures.

Notification of death must include a detailed narrative (death letter) that provides detailed information describing the circumstances surrounding the death and is signed by the principal Investigator or authorized co-Investigator. The death letter must include all of the following:

- a) Date and time of death
- b) Place death occurred

- c) Immediate cause of death
- d) The relatedness of the death to the CelonProSleep *plus*, surgical procedure, clinical investigation, or subject condition.
- e) Whether or not the death was witnessed
- f) Device status and/or activity at the time of death
- g) Any other circumstances surrounding the death
- h) Approximate time interval from the initiating event to death (temporal course)
- i) Investigator or co-Investigator signature and date
- j) Any information listed above that is unavailable or unknown must be specified in the death letter. Also submit the following documentation:
 - If the subject expired in the hospital, A copy of the medical records for that admission (e.g. H & P, consults, test results, operative reports, and/or progress notes from the hospital chart)
 - Death certificate (if available)
 - Autopsy report (if applicable)
 - A copy of the most recent clinic visit (if not already submitted to Sponsor)
 - Death certificate (if available)
 - Obituary (if able to obtain)

Data collected from the subject up to the point of death will remain documented on CRFs and/or worksheets. In addition to the Patient Status Change CRF, these may include the adverse event forms (if applicable), and Device Status Change CRF.

CelonProSleep *plus* and related Sponsor system components (e.g., probe) should be removed intact and returned promptly to Sponsor for analysis.

11.0 PROTOCOL DEVIATIONS/MODIFICATION

An Investigator is required to conduct this study in accordance with the signed Investigator's Agreement, this investigational protocol, applicable laws and regulations, and any conditions of approval imposed by the reviewing IRB/MEC.

The Investigator shall notify the Sponsor and the reviewing IRB/MEC of any deviation from the investigational plan to protect the life or physical well-being of a subject in an emergency. Such notice shall be given as soon as possible, but no later than five working days after the emergency occurred. Except in such an emergency, prior approval by the Sponsor is required for a change in or deviations from this plan and, if these changes or deviations could affect the scientific soundness of the plan or the rights, safety or welfare of human subjects, IRB/MEC and national authority approval is also required.

All deviations from the investigational plan must be reported to Sponsor, together with the reason for the deviation. In some circumstances, the center may be required to notify the center's IRB/MEC and Sponsor will notify the national authorities and/or suspend the center's participation in this clinical trial. In these circumstances, Sponsor will perform a compliance visit to evaluate adherence to the investigational plan, compliance with applicable regulations, and any additional specific issues related to the event. Additional training on the protocol and related procedures may also be necessary. At this time Sponsor will ask the Investigator to review the Investigator Agreement and applicable regulations regarding medical device clinical studies, specifically Investigator responsibilities.

12.0 DATA QUALITY ASSURANCE

12.1 Required Data

All required data for this trial will be collected on standardized case report forms (CRFs) designed specifically for the study. In general, the CRFs will be completed by a trained clinical research coordinator at the investigational site. Worksheets may be used to collect information that is not commonly recorded in medical records. Otherwise, all data should be corroborated by clinic or hospital records. Source documents must be available for review during monitoring visits. In the case of patient questionnaires, the CRF may be completed by the subject or the subject may complete a worksheet with the data then being transferred to a CRF by the clinical research coordinator, depending on the accepted practice at the site.

12.2 Monitoring Procedures

The study will be administered by the Department of Otolaryngology at the Medical University of South Carolina, and two other sites to be determined, and will require approval and monitoring by the sponsor.

Each site will allow Olympus Winter & Ibe, the Sponsor of the study and an independent CRO, to monitor the study activities and records to ensure that all investigators are in compliance with 1) appropriate regulatory requirements, 2) recommendations guiding physicians in biomedical research involving human subjects adopted by the 18th World Medical Assembly, Helsinki, Finland, 1964 and later revisions, 3) the protocol, and 4) the investigator's agreement.

Study sites will be monitored to ensure completed case report forms match the Sponsors records and to resolve any differences. Original source-documents will be kept in patient charts at the investigator's site and will be available for verification during monitoring or regulatory agency audit.

The monitor's responsibilities include: maintaining regular contact with each investigational site, through telephone contact and on-site visits, to ensure that the investigational plan is followed; that complete, timely and accurate data are submitted; that problems with inconsistent and incomplete data are addressed; and that the site facilities continue to be adequate.

The Sponsor will review significant new information, including unanticipated adverse events, and ensure that such information is provided to the investigators, and IRB's, as appropriate.

The Investigator(s) will ensure that an informed consent form is signed by each patient prior to study enrollment. Informed consents will be obtained according to individual institutional guidelines. These documents will be audited to ensure they have been signed prior to the RFA procedure and that the correct version was used.

Standardized case report forms must be completed for all patients enrolled into the study. Completion of standard case report forms will be required by all participating centers. The case report form should be a complete and accurate record of the patient's data collected during the study according to GCP recommendations. It is the responsibility of the investigator to ensure the quality of the data collected and recorded.

The case report forms will be reviewed for errors, omissions, internal consistency, and to ensure that the investigator has signed and dated the appropriate sections. Data entry will be done in a manner to ensure accuracy and the entered data will be audited for verification and validation purposes.

12.3 Patient Data Protection

All information and data concerning patients or their participation in this trial will be considered confidential. Only authorized personnel will have access to these confidential files. All data used in the analysis and reporting of this study will be without identifiable reference to the patients.

12.4 Ethical and Regulatory Considerations

The study will be performed in accordance with Good Clinical Practices and recommendations guiding physicians in biomedical research involving human subjects adopted by the 18th World Medical Assembly, Helsinki, Finland, 1964 and later revisions.

The protocol and informed consent will be reviewed and approved before enrollment of patients by the appropriate Institutional Review Board where the study will be conducted.

13 ROLES AND RESPONSIBILITIES

13.1 Role of the Sponsor Representatives

Olympus Winter & Ibe will serve as the Sponsor of this study. A Sponsor is defined as a person or organization that initiates, but does not actually conduct, the investigation (FDA regulation 21 CFR 812.3(n)).

Olympus Winter & Ibe personnel may provide technical support to the investigator and other health care personnel (collectively HCP) as needed during surgical procedures. Support may include HCP training, addressing HCP questions, or providing clarifications to HCPs concerning the operation of Olympus equipment.

At the request of the Investigator and while under their supervision, Olympus personnel may assist with operation of the equipment during treatment of study subjects. Typical tasks may include:

- Clarifying device setup and operation as requested by the Investigator or other health care personnel
- Observing testing or medical procedures to obtain information relevant to protocol compliance
- Reviewing collected data and study documentation for completeness and accuracy

Olympus Winter & Ibe personnel will not:

- Practice medicine
- Provide medical diagnosis
- Independently collect critical study data (defined as primary or secondary endpoint data)

13.2 Investigator's Role and Responsibilities

13.2.1 Clinical Investigators

The Investigator is responsible for conducting the study in accordance with the signed agreement, the investigational plan, applicable laws, the latest version of the “Declaration of Helsinki: Recommendations Guiding Medical Doctors in Biomedical Research Involving Human Patients” and any conditions of approval imposed by the reviewing regulatory body.

The clinical investigator shall be responsible for the day to day conduct of the clinical investigation as well as for the safety and well-being of the human subjects involved in the clinical investigation.

The clinical investigator shall have the resources to conduct the clinical investigation properly and obtain from the sponsor the information which he judges essential about the device and be familiar with this information.

The clinical investigator shall ensure that adequate information is given to the subject both in oral and written form, on the nature of the clinical investigation. This information shall be easily understandable by the subject. This information shall include the aims, expected benefits for him and/or others, risks and inconveniences and an explanation of any alternative methods, and of possible consequences of any withdrawal from the clinical investigation. Subjects shall be allowed sufficient time to decide whether or not they wish to participate. The subjects shall be informed that his/her participation in the clinical investigation is completely voluntary and confidential. The subject shall be made aware that the data relating to the study may be made available to third parties while maintaining anonymity.

The investigators must obtain a written IRB approval prior to including any patients into the study.

13.2.2 Investigator Selection

This study will be conducted by qualified Investigators who have experience with obstructive sleep apnea diagnosis and treatment, including knowledge of alternative therapy efficacy. The Investigator may have direct experience with the use of CelonProSleep *plus*. A principal Investigator and his/her sub-Investigator must be experienced in and responsible for: selection and evaluation of patients, strict adherence to this investigational protocol, which includes all testing requirements to provide for optimal safe and efficacious use of the CelonProSleep *plus*, collection of patient consent and study data, and submission of death letters, notes, etc.; if applicable.

It is acceptable for the Principal Investigator to delegate one or more of the above functions to an associate or sub-Investigator who is a trained healthcare professional, and who is trained on the study

Seite 46 von 54

Protocol 990211 RAMOSA

RFA for multi-level OSA

Protocol version 6.0 from 26th September 2014

protocol according to their role in the study. However, the principal Investigator remains responsible for proper conduct of the study. The study is not transferable to other centers attended by the Investigator unless prior approval is obtained from the Sponsor and the appropriate reviewing institutional oversight committee and regulatory body as required.

13.3. Study Initiation

Before participating in the clinical trial, each Investigator and sub-Investigator is required to submit to Sponsor a signed Investigator's Agreement. Prior to the Investigator's participation, the Investigator must forward written approval from the appropriate reviewing IRB to Sponsor.

13.4 Clinical Events Committee (CEC)

A Clinical Events Committee, consisting of independent physicians, will review all adverse events at regular intervals. The CEC is responsible for reviewing the Investigator's assessment and classification of each event. The CEC will also adjudicate subject withdrawals to determine whether therapy efficacy constituted a reason for their withdrawal. Study withdrawal due to therapy failure will be included in primary secondary analysis.

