3.1.1 Experimental Design

This is a single-arm assessment of AHI responder rate for treatment of obstructive sleep apnea compared to a performance goal (PG). Patients with 6-month post-treatment AHI measurements will be counted as a responder if they meet the performance goal. A subject will be counted as a non-responder (regardless of AHI measurement at 6 months) under the following circumstances:

- a. Death (any cause) between treatment and the 6-month follow-up
- b. Unsuccessful radiofrequency treatment attempt
- c. Need for an alternative OSA treatment before the 6-month follow-up
- d. Subjects who abandon the study
- e. Subjects who exit the study after the last treatment, but before the 6-month follow-up

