3.1.2 Subjects included in the Primary Efficacy Objective Analysis

The primary efficacy analysis will include all subjects who received all three radiofrequency treatment procedures and the follow-up assessment at 6-months post-treatment.

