8.5 Handling of Missing Data, Subject Withdrawals, and Treatment Failures

Subjects that are lost-to-follow-up will be categorized as treatment failures from the time point of dropout forward. Sensitivity analyses will also be conducted excluding lost-to-follow-up subjects to see what impact, if any, they might have on the overall results of clinical activity. Time-to-event analyses will consider these subjects as censored at the lost-to-follow-up time point. All data will be recorded on a CRF forms and will be subjected to regular monitoring.

Every effort will be made to follow subjects for study observation and encourage compliance with study measurements to minimize the amount of missing data.

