13.7 Withdrawal

The only reason for patient withdrawal from this study is patient request.

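### Section 13.4 ties inclusion of a withdrawal to its adjudicated cause, and this is not reconciled with 3.1.1 (all withdrawals are non-responders) or with 3.1.2 and 8.4 (none are analysed)

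*Combined protocol and SAP*

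**What the plan says.** Section 13.4 gives the committee a task beyond adverse events: "The CEC will also adjudicate subject withdrawals to determine whether therapy efficacy constituted a reason for their withdrawal". The consequence follows in the next sentence: "Study withdrawal due to therapy failure will be included in primary secondary analysis". Nothing is said about withdrawals put down to other causes.

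Section 3.1.1 introduces its list with "A subject will be counted as a non-responder (regardless of AHI measurement at 6 months) under the following circumstances". Item d is "Subjects who abandon the study" and item e is "Subjects who exit the study after the last treatment, but before the 6-month follow-up". Neither carries a condition on cause.

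Section 3.1.2 defines the analysed subjects differently: "The primary efficacy analysis will include all subjects who received all three radiofrequency treatment procedures and the follow-up assessment at 6-months post-treatment". The full analysis set (FAS) in 8.4 is also a completer set, because it requires all 8 visits.

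Section 8.5 says: "Subjects that are lost-to-follow-up will be categorized as treatment failures from the time point of dropout forward". Its heading mentions withdrawals, but its rule is written for subjects lost to follow-up.

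Section 13.7 adds: "The only reason for patient withdrawal from this study is patient request". Section 8.1 takes the responder proportion among all included subjects and names no analysis set.

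**The concern.** Adjudicating cause and then stating that therapy-failure withdrawals are included makes sense mainly if other withdrawals may be left out. The plan gives the adjudication no other analytic purpose. That sits badly with 3.1.1, where cause is irrelevant.

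A subject without a 6-month PSG cannot be a responder, so each withdrawal left out of the denominator raises the responder rate. The study is open-label with a single arm and a fixed 50% performance goal, so no comparator arm absorbs the effect. The documents give the CEC no criteria for deciding that efficacy was a reason for leaving. If 13.4 governed, the primary result could rest on one or two such decisions.

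**Working it through.** **The rules side by side, for a subject who withdraws before the 6-month PSG**

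- 3.1.1 (d, e): in the denominator as a non-responder, whatever the cause.
- 3.1.2 and the 8.4 FAS: not in the denominator, whatever the cause.
- 13.4: included if the CEC finds therapy failure; otherwise not stated.

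Section 8.2 mentions intention-to-treat and as-treated analyses of all enrolled subjects, but does not say which is primary.

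**Inputs.** Null 0.50 (3.1.3). Alternative 0.70, target one-sided alpha 0.025, n = 43 and 48 after 10% dropout (3.2). One-sided 97.5% interval (3.1), but one-sided 95% interval with an exact binomial p-value (8.1).

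**The plan's own figure.** The Z rule rejects if (x/n − 0.5)/√(0.25/n) ≥ 1.96. At n = 43, x = 28 gives z = 1.98 and x = 27 gives 1.68, so 28 responders are needed. P(X ≥ 28 | 43, 0.5) = 0.0330 and P(X ≥ 28 | 43, 0.7) = 0.8081. Both match section 3.2. Dropout: 43/0.9 = 47.8, rounded up to 48, which leaves 48 − 43 = 5 withdrawals.

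**Varying the number of withdrawals counted.** Assume 48 treated, 43 completers and 5 withdrawals. Let k of the 5 be attributed to therapy failure and scored as non-responders, so n = 43 + k. The split k is an assumption, shown over its whole range. Exact p is P(X ≥ 29 | n, 0.5). Power is the probability that 43 completers, each responding with probability 0.70, reach the required count.

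| k | n | Needed, Z rule | Needed, exact 0.025 | 29/n | Exact p at 29 | Power, Z | Power, exact |
|---|---|---|---|---|---|---|---|
| 0 | 43 | 28 | 29 | 67.4% | 0.016 | 0.808 | 0.708 |
| 1 | 44 | 29 | 29 | 65.9% | 0.024 | 0.708 | 0.708 |
| 2 | 45 | 30 | 30 | 64.4% | 0.036 | 0.587 | 0.587 |
| 3 | 46 | 30 | 31 | 63.0% | 0.052 | 0.587 | 0.456 |
| 4 | 47 | 31 | 31 | 61.7% | 0.072 | 0.456 | 0.456 |
| 5 | 48 | 31 | 32 | 60.4% | 0.097 | 0.456 | 0.327 |

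With 29 responders, the result at one-sided 0.025 changes between k = 1 and k = 2. At one-sided 0.05 it changes between k = 2 and k = 3.

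**False-positive side.** Suppose the true rate among all 48 treated is exactly 50% and every withdrawal is a non-responder. The completer rate is then 0.50 × 48/43 = 0.558. The chance of passing the Z rule is P(X ≥ 28 | 43, 0.558) = 0.141 if no withdrawal is counted, and P(X ≥ 31 | 43, 0.558) = 0.021 if all five are.

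**The case against.** The strongest reply is that 13.4 states inclusion and never exclusion. Read literally it is compatible with 3.1.1: if every withdrawal is a non-responder, those due to therapy failure are included as well. The key phrase is also garbled and could mean the primary analysis, the secondary analyses or both. This stands. A reader might infer that a withdrawal enters only if the CEC blames efficacy, but the text does not say so.

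A reader might also infer that the CEC's judgement does set the primary denominator. The documents do not support that. Under 3.1.1, 3.1.2 or the 8.4 FAS the judgement changes nothing; it matters only if a sentence in a committee-roles section overrides them, and no section says it does. Measured against 3.1.2, 13.4 adds failures back, which is conservative.

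Three further limits hold. Section 8.5 cannot be cited as scoring every withdrawal, because its rule covers subjects lost to follow-up; the cause-blind rule rests on 3.1.1. Section 13.7 does not show that the CEC would have to guess: it may mean only that the patient alone can initiate withdrawal, and the plan names a Patient Status Change CRF (10.6) and an End of Study Form (Appendix I) whose contents are not shown. The CEC consists of independent physicians, which reduces the risk of bias, although it supplies no attribution criteria.

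The size also depends on the decision rule. At exact 0.025 the first attribution changes nothing, since 29 responders are needed at both k = 0 and k = 1. At one-sided 0.05, 29 responders still pass at k = 2.

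None of this reconciles the sections. The completer definitions would drop even the therapy-failure withdrawals that 13.4 includes, so correcting 3.1.2 alone would leave 13.4 unresolved.

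**Conclusion.** The point holds as an unreconciled conflict. The plan contains three incompatible treatments of withdrawals (all count, none count, depends on adjudicated cause) and no order of precedence. Section 13.4 could set the primary denominator; it is not shown to do so.

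If it were applied at the planned dropout, the number of withdrawals counted could reverse the conclusion for results near the threshold, and it moves power over the ranges tabulated above. These figures assume exactly 5 withdrawals, all without a 6-month result, and a 70% response among completers. The reversal point depends on whether one-sided 0.025 or 0.05 is used, which 3.1 and 8.1 leave open. The conflict should be resolved before the data are analysed.

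**What to change.** Replace the last sentence of 13.4 with wording such as: CEC attribution of the reason for withdrawal is descriptive, or is used only in a labelled sensitivity analysis; every withdrawal before the 6-month PSG is a non-responder in the primary analysis, as in 3.1.1 (d, e), whatever the attributed reason.

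Change 3.1.2 and the 8.4 FAS at the same time, so that the primary set contains all treated subjects and the completer analysis becomes a sensitivity analysis. Editing 13.4 alone would contradict both. Make the text of 8.5 cover withdrawals as its heading does, and name the primary set in 8.1.

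The cost is a few sentences, a lower reported responder rate, and a restated power. The 80.8% in 8.3 applies only if the 70% rate holds among completers and no withdrawal is scored as a failure. With 5 withdrawals scored as failures, the corresponding figure is 0.46 under the Z rule or 0.33 under the exact 0.025 rule. The sponsor should therefore state which population the 70% refers to and check whether 48 subjects remain enough.
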